14.1.3. Interim Analysis

No interim analysis for early stopping is planned for the VenaSeal vs. ETA Study or the VenaSeal vs. Surgical Stripping Study.

14.1.4. Analysis Sets

The primary analysis set for Randomized Studies will be the ITT analysis set. Per-protocol (PP) analyses may be performed as a sensitivity analysis. All analysis sets have been defined with the intent of minimizing bias in the data analysis.

Intent-to-Treat (ITT): All patients who are randomized in the arms in each study will be included in the analysis regardless of the treatment received or the outcome of the treatment.

Per-Protocol (PP): The ITT population excluding failed and no procedure treatment outcomes, subjects that are treated with the modality they were not randomized to and/or have not met the inclusion/exclusion criteria.

As treated (AT): Includes subjects in the arm they are treated with according to the treatment actually received, regardless of the arm they were randomized to.

14.2. VLU Study (Single-Arm Study)

Analyses will be performed on all enrolled patients with CEAP 6 as according to the inclusion/exclusion criteria.

Descriptive statistics will be presented for the study endpoints.

14.2.1. Sample Size Consideration

The primary endpoint in the VLU Study is time to ulcer healing. For reference, the EVRA study³⁸ evaluated clinical and cost effectiveness of early endovenous treatment and standard care vs. deferred intervention in patients with chronic venous ulceration. As there are no statistically powered hypotheses in the VLU Study, precision estimates (distance from point estimate to the max of lower or upper 95% two-sided confidence bound) were used to derive the sample size based on the outcomes of the EVRA study.

In comparison to the EVRA study, criteria for VLU Study inclusion is less restrictive, which may result in an ulcer population which is older and heals more slowly than the EVRA early-intervention group. Precision calculations utilized an assumed median time to healing of 70 days which is the approximate average of the median healing time between the EVRA early-intervention and deferred-intervention groups (56 and 82 days, respectively). Precision estimates for a range of sample sizes are provided in **Table 20**. A simulation is run 10,000 times on the assumption of exponential distribution of 70 days median time to healing. The simulation result shows the precision of less than 23 days can be obtained with a sample size of 125 subjects enrolled into the VLU Study.

Table 20: Sample Size for the VLU Study

Sample size	Evaluable Sample Size (10% attrition)		Precision
	80	72	
90	81		<28 days
100	90		<26 days
110	99		<25 days
115	104		<24 days
120	108		<24 days
125	113		<23 days

14.2.2. Interim Analysis

No interim analysis is planned for this CEAP 6 single arm study.

14.2.3. Analysis Sets

Intention-to-Treat (ITT): All patients with CEAP 6 who are enrolled in this study (either successful, incomplete or failed treatment outcome) will be counted in the ITT population, which will be the primary analysis set.

Per-Protocol (PP): The ITT population excluding failed treatment outcome and/or subjects that have not met the inclusion/exclusion criteria

The primary analysis for this CEAP 6 single arm study will be on intention-to-treat (ITT) population. All analysis sets have been defined with the intent of minimizing bias in the data analysis.

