After the patient has signed the ICF, met all of the inclusion and none of the exclusion criteria, the CEAP 2-5 subjects will be randomized to one of the treatment arms, refer to section 10.4, Randomization and Treatment Assignment (CEAP 2-5) for more details. CEAP 2-5 subjects will be considered 'enrolled' from the moment of randomization.

CEAP 6 Subjects

CEAP 6 subjects that have met all of the inclusion and none of the exclusion criteria and sign the ICF will be considered 'enrolled' from the moment the first component of the VenaSeal™ delivery system enters the body. Study sites that are not identified at site selection as VLU sites will not be allowed to enroll CEAP 6 patients.

Treatment Outcome Groups:

The subjects will be included in one of the below treatment groups; the required follow-up schedule for all outcome groups is indicated in **Table 5**. In the event that the assigned treatment for the subject is not successfully completed on the first attempt, the reattempt of the procedure can be done on the same day or within 14 days of attempted index procedure per treating physician's discretion. After 14 days, the site should contact the study team to determine next steps.

Table 5: Treatment Outcome Groups

Treatment Outcome	Required Follow-Up
Successful Treatment*: Completion of the assigned treatment including any reattempt to complete the index procedure.	Follow subject schedule per schedule of events and data collection in section 10.1.
Incomplete Treatment*: The index procedure was commenced where the device entered the vasculature, or the surgical stripping procedure was initiated but for any reason full target vein length was not treated.	Follow subject schedule per schedule of events and data collection in section 10.1.
*Subjects with more than one target vein can have a resulting outcome of successful treatment in one vein and incomplete treatment in another. These differing outcomes should be reported on separate Procedure Target Vein CRFs.	

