Aborted Procedure: Failed completion of the assigned treatment where the subject was prepped for the index procedure, but the device did not enter the vasculature or surgical stripping was not initiated for any target vein.	Follow subject for 30 days from the date of the attempted index procedure for AE assessment only, which can be completed as a phone call visit if deemed appropriate by the treating physician. Any data collected prior to and during the attempted index procedure, including AE and device deficiency, should be reported on applicable CRFs.
No Procedure (CEAP 2-5): Subject is randomized (considered enrolled) but withdraws from the study after randomization without any attempt to conduct the procedure (e.g., COVID-19 exclusion, subject withdrawal, etc.).	Subject will not be followed in the study for any duration and can exit the study. Complete Study Exit CRF.
Randomization Procedure Not Followed (CEAP 2-5; major protocol deviation): Subject treated with a modality they were not randomized to.	Follow subject schedule per schedule of events and data collection in section 10.1. Report protocol deviation as "randomization procedure not followed".

[figure not shown]

Figure 3: Flow-Diagram from Subject Screening to Follow-up

Medtronic Business Restricted

CONFIDENTIAL

056-F275, v B Clinical Investigation Plan Template

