Appendix B: Definitions

Term	Definition
Aborted Treatment	Failed completion of the assigned treatment where the subject was prepped for the index procedure, but the device did not enter the vasculature or surgical stripping was not initiated.
Acute superficial thrombophlebitis	Thrombus induced inflammation of a vein in a time period <14 days from symptom onset. It presents with skin redness and tenderness around the hardened vein due to the associated inflammation. It is also commonly referred as superficial vein thrombosis.
Adjunctive treatment	Secondary treatment (phlebectomy and/or sclerotherapy) used to treat remaining varicosities after index procedure for cosmesis, to lessen the risk of superficial thrombophlebitis or because it may enhance primary treatment effectiveness.
As Treated (Analysis set for CEAP 2-5 subjects)	Includes subjects in the arm they are treated with according to the treatment actually received, regardless of the arm they are randomized to.
Circumferential ulcer	An ulcer that extends around the circumference of the leg and out of sight and, or an ulcer that cannot be captured in a single photograph with equipment provided by ulcer core laboratory.
COVID-19	Corona Virus Disease 2019, a new contagious disease caused by the Severe Acute Respiratory Syndrome Corona Virus 2 (SARS-CoV-2).
Endothermal Ablation Treatment (ETA)	Radiofrequency or laser ablation treatment available per site standard practice for the treatment of superficial venous reflux.
Granuloma	A grouping of macrophages. Non-specific.
Hypersensitivity reaction	An allergic reaction to a foreign body/substance.
Incomplete Treatment	The index procedure was commenced where the device entered the vasculature, or the surgical stripping procedure was initiated but for any reason full target vein length was not treated.

*Medtronic Business Restricted***CONFIDENTIAL**

VENASEAL SPECTRUM Clinical Investigation Plan

MDT18034

Version 5.0

Page 149 of 164

Medtronic

Intent to Treat (ITT) (Randomized studies; CEAP 2-5 subjects)	All patients who are randomized in the study will be included in the randomized arm in the analysis regardless of the treatment received.
Intent to Treat (ITT) (VLU Study; CEAP 6 subjects)	All patients with CEAP 6 who are enrolled in this study and successfully treated with VenaSeal™ system, will be counted in the ITT population.

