7.1.3 Analysis Sets

CEAP 2-5 randomized studies

The primary analysis set for Randomized Studies will be the ITT analysis set. Per-protocol (PP) analyses may be performed as a sensitivity analysis. All analysis sets have been defined with the intent of minimizing bias in the data analysis.

Intent-to-Treat (ITT): All patients who are randomized in the arms in each study will be included in the analysis regardless of the treatment received or the outcome of the treatment.

Per-Protocol (PP): The ITT population excluding failed and no procedure treatment outcomes, subjects that are treated with the modality they were not randomized to and/or have not met the inclusion/exclusion criteria. A failed procedure with no procedure treatment outcomes is defined as a procedure where the procedure treatment was never attempted or a procedure that was aborted.

As treated (AT): Includes subjects in the arm they are treated with according to the treatment actually received, regardless of the arm they were randomized to.

VLU (single arm) Study

Intention-to-Treat (ITT): All patients with CEAP 6 who are enrolled in this study (either successful, incomplete or failed treatment outcome) will be counted in the ITT population, which will be the primary analysis set.

Per-Protocol (PP): The ITT population excluding failed treatment outcome and/or subjects that have not met the inclusion/exclusion criteria. A failed procedure with no procedure treatment outcomes is defined as a procedure where the procedure treatment was never attempted or a procedure that was aborted.

The primary analysis for this CEAP 6 single arm study will be on intention-to-treat (ITT) population. All analysis sets have been defined with the intent of minimizing bias in the data analysis.

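### Protocol Appendix B limits the VLU intention-to-treat set to successfully treated subjects, contradicting protocol 14.2.3 and SAP 7.1.3; the VLU per-protocol treatment exclusion is also worded two ways and removes almost nobody

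*Protocol*

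**What the plan says.** **ITT, VLU Study.** Protocol 14.2.3 says that all CEAP 6 patients "enrolled in this study (either successful, incomplete or failed treatment outcome) will be counted in the ITT population", and names this the primary analysis set. SAP 7.1.3 carries the same definition. Protocol Appendix B instead says: "All patients with CEAP 6 who are enrolled in this study and successfully treated with VenaSeal™ system, will be counted in the ITT population".

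**Per-protocol (PP), VLU Study.** Protocol 14.2.3 defines it as "The ITT population excluding failed treatment outcome and/or subjects that have not met the inclusion/exclusion criteria". SAP 7.1.3 repeats this and adds that a failed procedure is "defined as a procedure where the procedure treatment was never attempted or a procedure that was aborted". Appendix B has one PP entry for CEAP 2-6. It removes subjects not treated with their assigned modality and those who did not meet the eligibility criteria.

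**Enrolment and outcomes.** Under protocol 9.2 a CEAP 6 subject counts as enrolled "from the moment the first component of the VenaSeal" delivery system enters the body. Table 5 in the same section describes an aborted procedure as one where the subject was prepared but "the device did not enter the vasculature or surgical stripping was not initiated for any target vein". It describes incomplete treatment as one where the device entered the vasculature but the full target vein length was not treated.

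**Use.** SAP 7.9.2.1.5 applies ITT with available data to the primary analysis of time to ulcer healing, and PP to the secondary analysis.

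**The concern.** The VLU Study has one arm and no hypothesis test. Its primary result is a Kaplan-Meier curve and a median time to healing, so the choice of subjects bears directly on the answer. A set restricted to successfully treated subjects selects on the outcome of the procedure. That is what an ITT label should rule out, yet Appendix B attaches the label to such a set. If limbs with residual untreated vein heal more slowly, dropping them shortens the reported median.

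The PP set is the planned secondary view of the same endpoint. A reader would expect its treatment exclusion to remove subjects whose procedure did not go as intended. As worded, the treatment failure that can occur after enrolment, incomplete treatment, stays in, and the exclusion acts on subjects who were almost never enrolled.

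**Working it through.** **1. ITT definitions side by side, by Table 5 outcome (CEAP 6)**

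| Outcome | Enrolled under 9.2? | ITT by 14.2.3 and SAP 7.1.3 | ITT by Appendix B |
|---|---|---|---|
| Successful | yes | in | in |
| Incomplete | yes, device entered the vasculature | in | out |
| Aborted | almost never, device did not enter the vasculature | in only if enrolled | out |

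The conflict falls mainly on the incomplete row.

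**2. What PP removes on treatment grounds**

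- SAP 7.1.3: failed means never attempted or aborted.
- Never attempted: no component entered the body, so the subject is not enrolled and not in ITT.
- Aborted: the device did not enter the vasculature. Such a subject is enrolled only if a component entered the body without reaching the vasculature. That gap is narrow but not nil.
- Incomplete: not listed as failed, so it stays in PP.
- Appendix B wording (not treated with the assigned modality): all VLU subjects are assigned VenaSeal, and enrolment requires a VenaSeal component in the body, so this too removes essentially nobody.
- Every PP wording still removes subjects who did not meet the inclusion/exclusion criteria.

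Table 5 has no outcome named failed. It uses the word only in describing an aborted procedure.

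**3. The plan's own VLU design figure**

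Protocol Table 20 states a precision below 23 days for 125 enrolled, 113 evaluable, with exponential healing times and a 70-day median. I ran 10,000 simulated samples with the SAP 7.9.2.1.4 order-statistic interval and took precision as the mean of the larger distance from the median to either bound. This gives 21.5 days at 113, so the stated figure reproduces. The definitional conflict does not make it wrong.

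**4. Illustrative shift in the median**

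The documents give neither the share incompletely treated, f, nor those subjects' median healing time, m. Both are assumed. With exponential healing in each group and 70 days in the successfully treated, the all-enrolled median t solves

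(1 − f) × 0.5^(t/70) + f × 0.5^(t/m) = 0.5

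| f | m = 105 | m = 140 | m = 210 |
|---|---|---|---|
| 5% | 71.3 | 72.1 | 73.1 |
| 10% | 72.7 | 74.4 | 76.4 |
| 15% | 74.1 | 76.8 | 80.0 |

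Check at f = 15%, m = 210, t = 80.0: 0.85 × 0.5^(80.0/70) + 0.15 × 0.5^(80.0/210) = 0.385 + 0.115 = 0.50.

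Appendix B would report 70 days in every cell, so the difference is about 1 to 10 days.

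**The case against.** The strongest reply is that the primary set is settled where the analysis is specified. Protocol 14.2.3 and SAP 7.1.3 agree, SAP 7.9.2 and 7.9.2.1.5 follow them, and Appendix B is an outlying glossary entry. An analyst would have to set aside both governing sections to lose the incomplete treatments. This stands as a limit on likelihood. It does not remove the contradiction: Appendix B is a stated rule in the current protocol, and I found no provision saying which wording prevails.

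The size is also wholly assumed, and two provisions may reduce it. A reattempt on the same day or within 14 days can still count as successful (protocol 9.2), and further superficial vein treatment required to heal the ulcer is permitted (protocol 9.4).

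Four stronger readings are tempting, and the documents do not support them.

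- **PP duplicates ITT.** It does not, because PP drops eligibility violators. The two sets would practically coincide only if there were none.
- **Protocol 14.2 gives a third ITT definition.** It says "Analyses will be performed on all enrolled patients with CEAP 6 as according to the inclusion/exclusion criteria". This can be read simply as CEAP 6 classified under the inclusion criteria, so it need not be a rival set.
- **The precision target fails under Appendix B.** With 5%, 10% and 15% removed, 113 evaluable becomes 107, 102 and 96, and the same simulation gives about 22.7, 22.7 and 24.2 days. The stated bound is exceeded only at the assumed 15%.
- **PP must exclude incomplete treatments.** No section says so, and the randomized studies' PP definition does not list them either. Excluding them would also select on a post-enrolment outcome.

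**Conclusion.** The point holds on two counts. First, Appendix B contradicts protocol 14.2.3 and SAP 7.1.3 on who is in the VLU primary analysis set, and as written it would remove incomplete treatments from the primary healing estimate. Second, the VLU PP treatment exclusion is nearly empty, is worded differently in Appendix B, and rests on a failed category that Table 5 does not name.

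The effect on the median arises only if Appendix B is applied and incompletely treated limbs heal more slowly. The illustrative 1 to 10 days rests on assumed shares of 5-15%, assumed medians of 105-210 days and exponential healing; it is not an estimate. The correction should be made before analysis, so that the denominator is not chosen after the data are seen.

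**What to change.** 1. Replace the Appendix B VLU ITT entry with the definition in protocol 14.2.3 and SAP 7.1.3: all enrolled CEAP 6 subjects, whatever the treatment outcome.
2. Use one VLU PP definition in protocol 14.2.3, Appendix B and SAP 7.1.3, separate from the shared CEAP 2-6 entry if need be.
3. In that definition, say which Table 5 outcome failed refers to, and whether Incomplete Treatment stays in PP. Keeping or excluding incomplete treatments is a choice for the sponsor. If they are excluded, say which vein decides, because Table 5 allows different outcomes in different target veins of one subject.

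The cost is wording in two protocol places and one SAP section. No new data are needed: Table 5 already has differing outcomes reported by vein on the Procedure Target Vein CRF. Steps 1 and 2 leave the primary analysis in the SAP unchanged. If incomplete treatments are excluded under step 3, the PP set becomes somewhat smaller.

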14.3. Analysis of Safety Events

Descriptive statistics for the safety events will be provided. Quantitative variables will be presented with mean and standard deviation or median, minimum and maximum as appropriate. Qualitative variables will be presented with frequency and percentage. The time-sensitive nature of any response variable may be displayed by using a Kaplan-Meier plot. AEs will be tabulated and reported using the current version of MedDRA dictionary. SAEs will be tabulated and reported up to 60 months.

14.4. Analysis of Baseline Characteristics

All clinically relevant baseline variables will be tabulated and reported. Quantitative variables will be presented with mean and standard deviation or median, minimum and maximum as appropriate. Qualitative variables will be presented with frequency and percentage.

14.5. Safety Event Analysis and Reporting of Results

Patient data listings and tabular and graphical presentations of results will be provided if needed.

14.6. Health Economics Analysis

This study will collect healthcare utilization data related to subject's VRD and care related to the VenaSeal™ closure system to demonstrate total costs over the follow-up period.

US cost and global effectiveness data collected in the study will be used to validate and update VenaSeal™ system US cost-effectiveness model developed by Medtronic. The healthcare utilization data from non-US countries will then be transformed to identified regional costs which will then be used as model parameters for global regional cost-effectiveness and/or budget impact model adaptations.

Specific analysis will focus on additional VLU healthcare utilization for all ulcers on the target limb, including routine wound care treatment through ulcer healing. The additional VLU healthcare utilization will not be only limited to routine wound care treatments but also any other unscheduled healthcare utilizations including office visits and emergency room visits.

14.7. Missing Data

Every effort will be undertaken to minimize missing data. Unless otherwise specified, no statistical techniques will be used to impute missing data for continuous or categorical outcomes. The number of patients included in each analysis will be reported so that the reader can assess the potential impact of missing data.

*Medtronic Business Restricted***CONFIDENTIAL**

056-F275, v B Clinical Investigation Plan Template

15. Ethics

15.1. Statement(s) of Compliance

The VenaSeal Spectrum study will be conducted in compliance with international ethical and scientific quality standards, known as Good Clinical Practice (GCP). GCP includes review and approval by an independent EC before initiating a study, continuing review of an ongoing study by an EC, and obtaining and documenting the freely given informed consent of a subject before initiating the study. This study is designed to reflect the GCP principles outlined in ISO 14155:2020 and other international clinical requirements outlined below. These include the protection of the rights, safety and well-being of human subjects, controls to ensure the scientific conduct and credibility of the clinical investigation and the definition of responsibilities of Medtronic and investigators. In accordance with ISO 14155:2020, Medtronic shall avoid improper influence on, or inducement of, the subject, monitor, any investigator(s) or other parties participating in, or contributing to, the clinical investigation. All investigators shall avoid improper influence on or inducement of the subject, sponsor, monitor, other investigator(s) or other parties participating in or contributing to the clinical investigation. The process of reporting AE and DD handling in this study is ISO 14155:2020 compliant for all participating geographies.

The study will be conducted according to the Clinical Investigation Plan, CTA, federal, national and local laws, regulations, standards, and requirements of the countries/geographies where the study is being conducted.

The study will also be conducted in accordance with the Declaration of Helsinki. The principles of the Declaration of Helsinki are implemented in this study by means of the patient informed consent process, IRB/EC/CA approval, study training and clinical study registration, risk-benefit assessment and publication policy.

Ultimately, all study sites in all geographies will follow and comply with:

- Principles of Declaration of Helsinki
- 21 CFR Part 11 (Electronic Records, Electronic Signatures)
- 21 CFR Part 54 (Financial Disclosure by Clinical Investigators)
- The CTA
- The procedures described within this CIP
- Local EC Requirements.

In addition to the regulatory requirements outlined above, the study will be conducted according to federal, national and local laws, regulations, standards, and requirements of the countries/geographies where the study is being conducted. These include but are not limited to:

Medtronic Business Restricted

CONFIDENTIAL

056-F275, v B Clinical Investigation Plan Template

- In the US, the study will be conducted in compliance with 21 CFR Parts 50 (Protection of Human Subjects) and 56 (IRBs).
- In Canada, SOR/98-282, Section 59-88 will be followed and Mandatory Problem Reporting 59(1), 59(2), 60(1).
- In Europe the study will be conducted in compliance with the MDD 93/42/EEC, EU MDR 2017/745.
- In all geographies except US, the study will be conducted in compliance with ISO 14155:2020, with an exception that this study only collects a subset of adverse events.

The study will be publicly registered prior to in accordance with 42 CFR part 11 and Declaration of Helsinki on <http://clinicaltrials.gov>. In addition, the study may be registered in local regulatory databases where required by local law.

Approval of the CIP and CIP amendments is required from the following groups prior to any study procedures at a study site:

- Medtronic
- Principal Investigators (where required by local law/regulations)
- Geography-specific regulatory authorities (if regulatory approval is required)
- An independent EC or IRB.

Similarly, approval of subsequent revisions to the CIP is required at each study site from the above mentioned groups prior to implementation of the revised CIP at the study site.

Due to the post-market nature of this study and because this study does not include a primary safety endpoint, the scope of AE reporting in this study has been limited to reporting of events listed in section 12 and no device accountability is required with exception of documenting a reference to the used device in the CRF (this is a deviation from ISO 14155:2020). The subject enrollment definition for this study is 'the moment of randomization' for CEAP 2-5 subjects and 'the moment the first component of VenaSeal™ system enters the body' for CEAP 6 subjects; this is also a deviation from ISO 14155:2020.

The EUDAMED generated single identification number of the clinical investigation will be provided under a separate cover when available.

16. Study Administration

